5.5 Subject Discontinuation

Each registered subject shall remain in the clinical investigation until completion of the required 90-day (\pm 30 days) follow-up visit however, a subject's participation in any clinical investigation is voluntary and the subject has the right to withdraw at any time

without penalty or loss of benefits. Conceivable reasons for discontinuation may include, but not be limited to, the following:

- Subject death
- Subject voluntary withdrawal
- Subject withdrawn by the Investigator
- Subject lost-to follow-up as described below
- Subject's follow-up is terminated according to **Section 3.3**.

The Sponsor must be notified of the reason(s) for subject discontinuation. The site will provide this information to the Sponsor. Investigators must also report this to their respective IRB as defined by their institution's procedure(s).

No additional follow-up will be required or data recorded from subjects once discontinued from the clinical investigation, except for the status (deceased/alive).

In case of subject withdrawal of consent, the site should make attempts to schedule the subject for a final clinical investigation visit prior to withdrawal. At this final follow-up visit, the subject will undergo the following assessments:

- Clinical assessment
- Echocardiographic assessment

Lost-to-Follow-up

There will be only one scheduled follow-up visit at 90 days (± 30 days) in this clinical investigation. If the subject misses the scheduled 90-day follow-up visit and the attempts at contacting the subject detailed below are unsuccessful, then the subject is considered lost-to-follow-up. Site personnel shall make all reasonable efforts to locate and communicate with the subject (and document these efforts in the source documents), including the following:

- A minimum of two telephone calls on different days over the specified follow-up window to contact the subject should be recorded in the source documentation, including date, time and initials of site personnel trying to make contact.
- If these attempts are unsuccessful, a letter (certified, if applicable) should be sent to the subject.

Note: Telephone contact with general practitioner, non-clinical investigation cardiologist or relative without the presence of the subject or indirect documentation obtained via discharge letters will not be considered as subject contact.

5.7 **Expected Duration of Each Subject's Participation**

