7.3 Adverse Event and Device Deficiency Reporting

7.3.1 Adverse Event Reporting

Safety surveillance and reporting starts as soon as the subject is registered in the clinical investigation. Safety surveillance and reporting will continue until the last follow-up visit has been performed, the subject is deceased, the subject concludes participation in the clinical investigation or the subject withdraws from the clinical investigation. All adverse event data, including deaths and device deficiencies, will be collected throughout the time period defined above and will be reported to the Sponsor on a CRF. Additional information with regard to an adverse event should be updated within the appropriate CRF.

Unchanged, chronic, non-worsening or pre-existing conditions are not AEs and should not be reported.

An offline form will be made available to allow the investigator to report SAEs in the event the entry cannot be made in the EDC. This does not replace the EDC reporting system. All information must still be entered in the EDC system as soon as feasible.

Non-cardiac related abnormal laboratory values will not be considered AEs unless:

1. The investigator determined that the value is clinically significant,
2. The abnormal lab value required intervention, or
3. The abnormal lab value required subject withdrawal from the clinical investigation.

In this clinical investigation, all adverse events, regardless of their relationship to the devices, are to be documented on the appropriate CRF throughout the 90-day follow-up visit. Anticipated adverse event definitions can be found in **Appendix II**.

SAE Reporting

The investigator should report all SAEs to the Sponsor as soon as possible but no later than the timelines outlined below.

Clinical Site	Reporting timelines
All Sites	SAEs must be reported to the Sponsor no later than 3 calendar days from the day the site personnel became aware of the event or as per the investigative site's local requirements, if the requirement is more stringent than those outlined above.

The date the site staff became aware the event met the criteria of an SAE must be recorded in the source document. The Investigator will further report the SAE to the local IRB according to the institution's IRB reporting requirements.

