1.4.1 Primary Endpoint

The primary endpoint of the clinical investigation is a composite endpoint at 90 days, including the following components representing important safety and effectiveness endpoints:

- Cardiovascular Death
- Myocardial infarction (MI)
- Stroke
- Any unplanned repeat revascularization (PCI or CABG)
- Bleeding (BARC 3 or 5) up to 14 days post-device removal
- Severe hypotension, defined as: systolic blood pressure (SBP) or augmented diastolic pressure (whichever is greater) <90 mmHg while on device support requiring (1) more than one administration of OR (2) continuous infusion of inotropic/pressor medications to restore hemodynamics
- Change in aortic insufficiency from baseline to 90 days by echocardiographic assessment and defined as:

| Baseline Assessment | 90 Day Assessment |
|---------------------|--------------------|
| None | Moderate OR Severe |
| Trace | Moderate OR Severe |
| Mild | Moderate OR Severe |

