2.2.3 Survival Analyses

Survival analysis will be conducted to analyze time-to-event variables. Subjects without events will be censored at their last known event-free time point. Subjects who withdrew from the study will be censored at the date of withdrawal. Survival curves will be constructed using Kaplan-Meier⁴ estimates. Summary tables for endpoints will include event (failure) rates, Greenwood standard error and confidence interval for the event rates.

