2.3 Endpoint Analysis

2.3.1 Primary Endpoint(s)

The primary endpoint, a composite of safety and effectiveness at 90 days, will be evaluated using the difference in event rates in the ITT population of the pivotal phase. The hypothesis test is designed to show non-inferiority of HeartMate PHP to Impella for the primary endpoint with one-sided alpha of 0.025.

[REDACTED]

ICER

[REDACTED]

If non-inferiority is met, superiority testing will be performed with a two-sided alpha of 0.05.

[REDACTED]

[REDACTED]

The data will be analyzed for superiority using Fisher's exact test.

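### The protocol keeps recording vital status after a subject leaves, but the SAP's survival rule censors withdrawn subjects at withdrawal and gives that information no use

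*Protocol*

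**What the plan says.** Protocol 5.5 (Subject Discontinuation) covers death, voluntary withdrawal, withdrawal by the investigator, loss to follow-up and study termination. For discontinued subjects it says: "No additional follow-up will be required or data recorded from subjects once discontinued from the clinical investigation, except for the status (deceased/alive". It states no date, no cause of death and no time limit for that status. Protocol 7.3.1 ends safety reporting at, among other points, the time when "the subject concludes participation in the clinical investigation or the subject withdraws from the clinical investigation".

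SAP 2.2.3 (Survival Analyses) is general in scope: "Survival analysis will be conducted to analyze time-to-event variables". It has two censoring sentences. The first is "Subjects without events will be censored at their last known event-free time point". The second is "Subjects who withdrew from the study will be censored at the date of withdrawal". On output it says: "Summary tables for endpoints will include event (failure) rates, Greenwood standard error and confidence interval for the event rates". It does not list the variables or endpoints concerned.

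The death component of the primary composite in SAP 1.4.1 is "Cardiovascular Death". SAP 2.3.1 says the composite "will be evaluated using the difference in event rates in the ITT population of the pivotal phase".

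**The concern.** The protocol goes on collecting one outcome after a subject leaves, and the survival rule then has no place for it. Censoring at withdrawal is harmless on average only if those who withdraw go on to die at the same rate as those who stay. In an open-label trial of high-risk patients, where the investigator may also withdraw a subject, that is not assured. For all-cause death the assumption is also unnecessary, because the trial intends to know the outcome.

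At stake is any secondary mortality estimate in a trial meant to support pre-market approval. Without a written rule, someone would have to decide after the data are in whether a known death after withdrawal counts.

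**Working it through.** **1. The two rules applied to one subject.** Take a subject who withdraws on day 20 and is later recorded as deceased, with the death on day 50. Under Protocol 5.5 the trial knows of the death. Under SAP 2.2.3 the subject is at risk to day 20 and censored there, and the death adds no event. If instead the subject is known to be alive at day 90, 90 - 20 = 70 days of known survival are lost. Both examples need a date, which Protocol 5.5 does not require. A bare deceased entry cannot be placed on a curve, and without a cause it cannot be classed as cardiovascular. So the gap lies in the protocol's data capture as well as in the SAP.

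**2. Expected shift.** The documents state no figure to reproduce here. Assumed inputs: 90-day mortality of 6% on study, a proportion w withdrawing at times uniform over 90 days, and a death hazard multiplied by h after withdrawal, with all later deaths known and dated. N = 473 is the minimum randomized number in SAP 2.4.

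- Cumulative hazard over 90 days: a = -ln(0.94) = 0.0619.
- Censoring at withdrawal estimates the on-study risk, 6.00%, whatever h is.
- Mean probability that an intended withdrawer survives to day 90: E(h) = exp(-ha) × [exp((h-1)a) - 1] / [(h-1)a], with E(1) = 0.94. This gives E(3) = 0.8842 and E(5) = 0.8327.
- True 90-day mortality: (1-w) × 0.06 + w × [1 - E(h)].
- Uncounted deaths: 473 × w × [0.9697 - E(h)], where 0.9697 = 0.06/a is the mean probability of being alive at withdrawal.

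| w | h | True mortality | Shift (points) | Uncounted deaths |
|---|---|---|---|---|
| 3% | 1 | 6.00% | 0 | 0.4 of 28.4 |
| 5% | 3 | 0.95 × 6.00 + 0.05 × 11.58 = 6.28% | -0.28 | 2.0 of 29.7 |
| 3% | 5 | 0.97 × 6.00 + 0.03 × 16.73 = 6.32% | -0.32 | 1.9 of 29.9 |
| 8% | 5 | 0.92 × 6.00 + 0.08 × 16.73 = 6.86% | -0.86 | 5.2 of 32.4 |

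Simulation of the same set-up agrees within its error (for w = 5% and h = 3: 6.25% true, against 5.96 to 5.98% by Kaplan-Meier). At h = 1 information is lost but there is no bias. For h below 1 the sign reverses.

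If one arm has 8% withdrawal, the other 3%, and h = 5 in both, the true difference is 6.86 - 6.32 = 0.54 points, and the censored curves would show a difference of about zero.

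**3. One hypothetical data set.** An arm of 315 has 8, 6 and 2 deaths on days 5, 20 and 70, and 9 withdrawals on day 15.

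- SAP rule: 1 - (1 - 8/315)(1 - 6/298)(1 - 2/292) = 5.16%.
- With 1, 2 or 3 dated deaths after withdrawal and everyone else known alive at day 90: 17/315 = 5.40%, 18/315 = 5.71%, 19/315 = 6.03%.

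The gap is 0.24 to 0.88 points. With 32 withdrawals and one later death it is only 0.02 points (5.37% against 5.40%). The later risk among the withdrawn, 1/32 = 3.1%, is then close to that of the 275 still followed, 8/275 = 2.9%.

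**4. Scale against sampling error.** At 6% mortality the standard error is √(0.06 × 0.94/473) = 1.1 points overall. For the difference between arms of 315 and 158 it is √(0.0564/315 + 0.0564/158) = 2.3 points.

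**The case against.** The strongest reply is that the affected output is inferred. A reader might conclude that the trial's Kaplan-Meier death rates are understated. The documents do not support that. No readable passage names such a rate, and the descriptive endpoint lists are redacted, so whether death has a curve at all depends on text that cannot be seen. Nor is understatement automatic, since it needs a higher risk of death after withdrawal than before.

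A reader might also infer that the primary result is affected. It is not affected by this rule. The composite is compared by a difference in event rates, with its own denominator rule in SAP 2.2.2 and the sensitivity analyses listed in SAP 2.12. SAP 2.11 states that there are no powered secondary endpoints.

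A third tempting inference is that later vital status is used for subjects lost to follow-up but thrown away for those who withdrew. The two sentences in SAP 2.2.3 are worded differently, but nothing says that later vital status moves the last event-free time of a lost subject.

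The withdrawal sentence can also be read as a special case of the one before it, covering event-free subjects only. That is reasonable, and for non-fatal or composite endpoints censoring at withdrawal is right, because being alive does not show freedom from MI, stroke or bleeding. But on that reading the rule still discards known survival time, and it does not say whether a death after withdrawal makes the subject one with an event. Finally, the illustrated shifts are small beside the standard errors and rest wholly on assumed inputs. That limits the importance of the point but does not resolve the mismatch.

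**Conclusion.** The mismatch is real and narrow. Vital status is kept after discontinuation, and no readable passage gives it a route into a survival analysis. As written, known deaths after withdrawal would go uncounted, and known survival would be discarded, in any Kaplan-Meier analysis that includes death. The point concerns subjects who withdrew, not everyone who discontinued, and secondary mortality estimates, not the primary test.

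Size and direction cannot be established from the documents. The range of 0 to about -0.9 points assumes 6% mortality, 3 to 8% withdrawal, a hazard ratio of 1 to 5 and complete, dated ascertainment. The change is worth making because it is cheap and settles before unblinding which deaths count.

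**What to change.** - **SAP 2.2.3:** limit censoring at withdrawal to non-fatal events. For all-cause death, count each death recorded under Protocol 5.5 up to day 90 as an event on its date. Otherwise censor at the last date known alive, up to day 90.
- **Protocol 5.5:** record with the status the date of death or the last date known alive. Add the cause of death where available, so that cardiovascular death can be adjudicated. Both apply as far as consent allows.

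The cost is a short SAP rule and a few extra fields on an existing entry. No visits or subjects are added.

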6.2 Randomization

6.2.1 Stratified Randomization

Subjects will be randomly assigned in a 2:1 fashion to either HeartMate PHP or Impella in SHIELD II.

[REDACTED]

[REDACTED]

6.2.2 Timing of Randomization

Randomization assignments will be given through EDC Study Site Portal after subjects have signed the ICF and met all eligibility requirements. Subjects will be considered registered in the clinical investigation once randomized and must follow all CIP

[REDACTED]

[REDACTED]

requirements. Randomized subjects who do not undergo device placement due to previously undiagnosed anatomic abnormalities (e.g. peripheral vascular disease) which precludes device placement, will be considered registered and in the intent-to-treat (ITT) population, and they must follow all CIP requirements. Once a subject is randomized, PCI should be performed as soon as possible.

6.3 Index Procedure

6.3.1 Right Heart Catheterization

Right heart catheterization is required to obtain hemodynamic measurements, and the placement of the catheter for the right heart catheterization will need to be done before inserting the study device and performing the PCI procedure for revascularization. In this CIP, the beginning of the index procedure is defined as the insertion of the first vascular access during the index procedure, and the end of the index procedure is defined as the removal of the last vascular access during the index procedure or the exit from the catheterization laboratory, whichever occurs first. In addition, the beginning of the PCI procedure is defined as the insertion of the first guiding catheter for the lesion(s) to be revascularized during this index procedure, and the end of the PCI procedure is defined as the removal of the last guiding catheter for the lesion(s) to be revascularized during this index procedure.

Hemodynamic Assessments

Hemodynamic assessments will be performed at the following four time points:

- 1) Prior to device insertion
- 2) Prior to the PCI procedure while on device support
- 3) Immediately prior to weaning for the preparation of device shutdown and removal
- 4) 10 to 30 minutes after device removal

The following hemodynamic measurements at each of the time points above and the corresponding study pump parameters at time points 2) and 3) above need to be collected and recorded:

- Right atrial pressure (RAP)
- Pulmonary artery pressure (PAP)
- Pulmonary capillary wedge pressure (PCWP)
- Cardiac output (CO)*
- Cardiac index (CI)*
- Cardiac power output (CPO)
- Mean arterial pressure (MAP)
- Heart rate
- Corresponding pump speed of PHP or Impella at time points 2) and 3)

- Corresponding estimated pump flow of PHP or Impella at time points 2) and 3)

***Note:** The Fick method is required to measure CO and CI. A second method using thermodilution can be optional.

Hemolysis Biomarker Assessment

Hemolysis biomarkers include plasma free hemoglobin and lactate dehydrogenase (LDH). Two blood draws during the index procedure are required for the assessment.

1. Pre-device draw: Blood will be collected before device insertion via a vascular access sheath (could be venous or arterial, and with no other catheter/device simultaneously inserted in the sheath) in the catheterization laboratory during the index procedure for the assessment of both plasma free hemoglobin* and LDH.
2. Post-device draw: Blood will be collected after device removal via a vascular access sheath (could be venous or arterial, and with no other catheter/device simultaneously inserted in the sheath) in the catheterization laboratory during the index procedure for the assessment of both plasma free hemoglobin* and LDH.

* **Caution:** Special attention must be paid to blood draw and processing before laboratory analysis to avoid hemolysis during or after blood draw, which will cause falsely elevated values in the plasma free hemoglobin test. 1) Collect blood from a vascular access sheath for both pre-device and post-device draws to avoid the shearing of red blood cells through a small-gauge (<18 gauge) needle. 2) Centrifuge immediately or as soon as possible to separate plasma or serum from red blood cells following blood collection.

6.3.2 Procedures Involved in the Use of the Study Device

HeartMate PHP and Impella are both temporary ventricular assist devices indicated for support during high-risk PCI. The study device (HeartMate PHP or Impella) will be inserted before the PCI procedure starts and will be removed after the PCI procedure ends. The preparation and use of the HeartMate PHP and Impella devices will be according to their respective IFUs.

HeartMate PHP and Impella device parameters will be collected and recorded on the appropriate electronic case report form (eCRF) in EDC. For the HeartMate PHP device, the data can be found on the console. For the Impella device, the data can be found on the automated Impella controller. All pump data collected should be kept in the patient binder.

If any issues occur with the use of the HeartMate PHP during the index procedure, the HeartMate PHP must be returned to Abbott after use. A device deficiency must be recorded as appropriate and as described in Section 7.3.3. After device removal in the catheterization laboratory, sites will record any gross device abnormalities (e.g., thrombus, cuts, tears, etc.) on the eCRF prior to shipment of the device to Abbott.

6.3.3 PCI Procedure for Revascularization

Completeness of Revascularization

All ischemic myocardial areas should be revascularized. The approach is to perform PCI of all significant ischemia-producing lesions as opposed to all lesions which appear to be significant by angiographic visual assessment. Moreover, it is strongly recommended that PCI is performed only in ischemia-producing lesions, in most cases not treating non-ischemia-producing lesions.

Ischemia-producing lesions are defined as those which are:

- 1) $\geq 70\%$ angiographic diameter stenosis (visually assessed), or
- 2) $<70\%$ diameter stenosis and:
 - a) associated with noninvasive functional evidence of ischemia in the territory of the lesion (not explained by another coronary stenosis), and/or
 - b) intra-procedure fractional flow reserve (FFR) ≤ 0.80 or an alternative intra-procedure physiological index (e.g., instantaneous wave free ratio (iFR) or resting full-cycle ratio (RFR) with the respective threshold defined per its IFU), and/or
 - c) intravascular ultrasound (IVUS) minimal luminal area $\leq 6.0 \text{ mm}^2$ (for left main lesions)

All lesions which the investigator has targeted/planned for revascularization will be identified and recorded on the eCRF prior to randomization for subjects in the randomized cohort or prior to the index procedure for subjects in the roll-in cohort by the interventionalist performing the procedure. All lesions that are actually revascularized will also be recorded on the eCRF.

Angiography and PCI Information

Angiography and PCI information will be collected on the appropriate eCRF. Angiograms of all treated lesions pre- and post-PCI must be performed following the guidance in the Angiographic Protocol from the Angiographic Core Laboratory and submitted to the core laboratory via Bioclinica website for analysis. For each treated lesion, the total number of stents used, the relevant stent information, and the guiding catheter size must be recorded on the appropriate eCRF. Any pre-dilation, post-dilation, or atherectomy device use on the lesion and the total volume of contrast used during the procedure must also be recorded. If a baseline diagnostic angiogram is not available for submitting to the Angiographic Core Laboratory for analysis, diagnostic views of all three major epicardial coronary arteries (left anterior descending (LAD), left circumflex (LCX), and right coronary artery (RCA)) need to be repeated prior to PCI during the index procedure for the core laboratory to calculate the SYNTAX score.

Additional data related to the index procedure may also be collected.

6.4 Post-Index Procedure Assessments

- Vital signs
- Laboratory tests except for cardiac biomarkers (must be performed within 24 hours post device removal; refer to **Table 2** for required post-procedure laboratory tests)
- Cardiac biomarkers: Both CK-MB and troponin (NO high-sensitivity troponin) are required for the post-procedural assessment.
 1. First draw at 6 to 12 hours post-device removal
 2. If CK-MB is elevated $> 1x$ ULN or troponin is elevated $> 7x$ ULN in the first draw, a second draw of CK-MB and troponin is required at 18-24 hours post-device removal or at the time of discharge as long as discharge is at or after 16 hours post-device removal.

Note: If CK-MB or troponin in the second draw is not stable and falling compared to the first draw, serial measurements of CK-MB and troponin every 12 hours or per site standard until a decline is noted are highly recommended.

- At least one 12-lead ECG (within 24 hours post device removal)
- Echocardiogram (must be performed within 48 hours post-device removal; may be performed during the procedure after device removal; performed per the Echocardiographic Core Laboratory guidance with images uploaded to the Echocardiographic Core Laboratory via Bioclinica website)
- Adverse event
- Concomitant use of anticoagulant and antiplatelet medications

For vital signs, laboratory tests and echocardiogram, refer to **Section 6.8** for further details.

